#### \*Study Design

This is an observational study utilizing prospectively collected electronic health record (EHR) data obtained from the OPERA® cohort. The study population will include treatment experienced PWH who are 18 years or older, are active in care in OPERA, and received at least one CAB+RPV LA injection between 21JAN2021 and 31DEC2023, 21JAN2021 and 31DEC2024, and 21JAN2021 and 31DEC2025. PWH will be followed from the date of their first CAB+RPV injection until discontinuation of CAB+RPV regimen, death, loss to follow-up (12 months after last clinical contact), or study end (29FEB2024, 28FEB2025, and 28FEB2026).

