#### **Censoring criteria:**

- Discontinuation of regimen of interest
- Death
- Loss to follow-up (12 months after last clinical contact)
- Study end (end of observation period: 29FEB2024, 28FEB2025, 28FEB2026)

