#### 6.3.2.4. Discontinuation

Discontinuation will be defined as >67 days after last injection (monthly dosing) or >127 days after last injection (every other month dosing).

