## 6.3.2.6. Virologic effectiveness

Among suppressed (VL< 50 copies/mL) at initiation:

Maintaining virologic suppression: Among PWH who were suppressed (VL <50 copies/mL) at baseline, the number and proportion who remain suppressed (VL <50 copies/mL) throughout all of follow-up will be reported, as well as the number and proportion who are suppressed (VL <50 copies/mL) at last follow-up. Proportion of individuals with VL <50 copies/mL during the first 6 months, and at 6, 12, 24, 36, 48, and 60 months following initiation of CAB+RPV LA regimen will be described.

Confirmed virologic failure: Confirmed virologic failure will be defined as 2 consecutive follow-up VLs ≥200 copies/mL OR 1 follow-up VL ≥200 copies/mL + discontinuation within 4 months of VL ≥200 copies/mL. The number and proportion of PWH with confirmed virologic failure will be reported as well as the time to virologic failure (months). Proportion of individuals with confirmed virologic failure (CVF) during the first 6 months, and at 6, 12, 24, 36, 48 and 60 months following initiation of CAB+RPV LA regimen will be described.

Among viremic ( $VL \ge 50$  copies/mL) at initiation:

Achieving virologic suppression: Among PWH who were viremic ( $VL \ge 50$  copies/mL) at baseline, the number and proportion who achieve a VL < 50 copies/mL at any point during follow-up will be reported, as well as the number and proportion who achieve a VL < 50 copies/mL at last follow-up. Proportion of individuals with VL < 50 copies/mL during the first 6 months, and at 6, 12, 24, 36, 48 and 60 months following initiation of CAB+RPV LA regimen will be described.

Non-response: VL ≥50 copies/mL after 6 and 12 months following initiation of CAB+RPV LA regimen and also no VL of <50 copies/mL during follow up will be described.

Confirmed virologic failure defined as:

- Suppressed to <50 copies/mL followed by either 2 VLs ≥200 copies/mL or
  1 VL ≥200 copies/mL and discontinuation within 4 months for every other month
  regimen; and discontinuation within 2 months for monthly regimen. Proportion of
  individuals with confirmed virologic failure (CVF) during the first 6 months, and at
  6, 12, 24, 36, 48 and 60 months following initiation of CAB+RPV LA regimen will
  be described.

- FDA's ask: Suppressed to <50 copies/mL followed by either 2 VLs ≥400 copies/mL

Protocol Final ViiV Healthcare 216990 - Amendment 2

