## 6.5. \*Study size

Over two years (21JAN2021 and 28FEB2023), there were 1,843 individuals who were 18 years of age or older with HIV-1 in OPERA who were active in care and had received their first CAB+RPV injection. Of these, 1,578 had viral loads <50 copies/mL at first injection, and 229 had viral loads ≥50 copies/mL (36 had no viral load data available at first injection). Study size is expected to grow for Year 3, Year 4, and Year 5 making these calculations underestimates.

Confidence intervals, constructed using the asymptotic (Wald) method based on a normal approximation, are presented in Table 1, and are designed to give estimates of precision for a variety of sample sizes and event probabilities.

The example sample sizes in Table 1 reflect the overall sample size as well as the strata based on viral load at first CAB+RPV LA injection.

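### People viremic at initiation who never suppress and discontinue before month 6 get neither failure label, so the count of labelled virologic failures in that stratum is short

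*Protocol*

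**What the plan says.** Protocol section 6.3.2.6 defines virologic outcomes separately by VL at initiation.

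**Viremic at initiation (VL of 50 copies/mL or more)**
- Non-response: "Non-response: VL ≥50 copies/mL after 6 and 12 months following initiation of CAB+RPV LA regimen and also no VL of <50 copies/mL", the last condition applying during follow-up. No denominator is given, and nothing is said about people whose follow-up ends before month 6.
- CVF, 200-copy version: "Suppressed to <50 copies/mL followed by either 2 VLs ≥200 copies/mL", or one such VL plus discontinuation within 4 months (every-other-month dosing) or 2 months (monthly dosing).
- CVF, 400-copy version: "FDA's ask: Suppressed to <50 copies/mL followed by either 2 VLs ≥400 copies/mL", with the same alternative limb.
- Achieving suppression: a VL below 50 at any point, at last follow-up, during the first 6 months and at fixed times from month 6 to month 60.

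**Suppressed at initiation**
- CVF: two consecutive VLs of at least 200, or one VL of at least 200 plus discontinuation within 4 months.

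**Follow-up.** The censoring criteria in section 6.2 include "Discontinuation of regimen of interest". The Synopsis says the same: "PWH will be followed from the date of their first CAB+RPV injection until discontinuation of CAB+RPV regimen, death, loss to follow-up" or study end. Section 6.3.2.4 sets discontinuation at more than 67 days (monthly) or 127 days (every other month) after the last injection. Section 6.3.2.3 reports VL at discontinuation, split at 200, for discontinuers with at least one follow-up VL.

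**The concern.** Non-response is the only failure label open to someone who starts viremic and never suppresses, because CVF in that stratum is defined as rebound. Yet the label can be earned only by staying on the regimen to month 6. Someone whose VL stays high and who stops earlier has an unfavourable course and no label.

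Virologic effectiveness is primary objective 3, and VL at initiation is a named subgroup. If the non-response count depends on who remains on treatment to month 6, counts from groups or data cuts with different early discontinuation are not comparable. The two strata also treat a similar event differently: a high VL followed by discontinuation is failure for a suppressed starter and is unlabelled for a viremic starter who never suppressed.

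**Working it through.** **1. Classification.** Take a person who is viremic at the first injection, has every VL at 50 or above, and discontinues before month 6.

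| Outcome (section 6.3.2.6 unless stated) | What it needs | Met? |
|---|---|---|
| Non-response | A VL of at least 50 after month 6, within follow-up | No: follow-up has ended |
| CVF, 200-copy version | An earlier VL below 50 | No |
| CVF, 400-copy version | An earlier VL below 50 | No |
| VL below 50 at any point | One VL below 50 | Not achieved; in the complement if all viremic starters are the denominator |
| VL at discontinuation (6.3.2.3) | At least one follow-up VL | Shown, split at 200, not labelled as failure |

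**2. Who falls in the gap.** Count the first injection as day 0 and month 6 as 365.25/2 = 182.6 days. If the discontinuation window counts as follow-up:
- Monthly: 182.6 − 67 = 115.6, so last injection by about day 115.
- Every other month: 182.6 − 127 = 55.6, so last injection by about day 55.

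One injection is enough for eligibility (section 6.2). A person with a single injection therefore reaches discontinuation on about day 68 or 128 and is always in the gap if never suppressed. If follow-up is instead closed at the last injection, the gap is wider. If values after both month 6 and month 12 are required, the limits move to 365.25 − 67 = 298 and 365.25 − 127 = 238 days.

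**3. Size.** The Protocol states no non-response or early-stopping rate, so it has no figure of its own to reproduce. The stratum size comes from section 6.5 ("229 had viral loads ≥50 copies/mL") and is consistent: 1,578 + 229 + 36 = 1,843.

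Let N = 229, A = non-responders as worded, and B = never-suppressed people who discontinue before month 6. A and B are assumptions. As worded the proportion is A/N; with B counted it is (A + B)/N.

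| A | A/N | B = 5 | B = 11 | B = 23 |
|---|---|---|---|---|
| 11 | 4.8% | 16/229 = 7.0% | 22/229 = 9.6% | 34/229 = 14.8% |
| 23 | 10.0% | 28/229 = 12.2% | 34/229 = 14.8% | 46/229 = 20.1% |

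The difference is B/N: 2.2, 4.8 or 10.0 percentage points.

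**4. Dependence on the denominator.** If only B leaves the denominator, A/(N − B) is still lower: with A = 23 and B = 11, 23/218 = 10.6% against 14.8%.

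If the denominator is everyone still followed at month 6, C early stoppers who did suppress leave it too. With A = 23 and B = 5:
- C = 46 (20% of 229): 23/(229 − 5 − 46) = 23/178 = 12.9%.
- C = 69 (30% of 229): 23/(229 − 5 − 69) = 23/155 = 14.8%.

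Both exceed the all-starter figure of 28/229 = 12.2%. The count is short by B whatever the denominator, but the proportion can err either way.

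**The case against.** **These people are not lost from the report.** A reader might infer that they drop out of every effectiveness measure, so that results improve as more early failures stop. The text does not support that. Suppression at any point and at last follow-up are framed among people viremic at baseline. On that wording, someone who never suppresses counts against both, however early they stop. Discontinuation is also stratified by VL at initiation (section 6.7.1.1), and VL at discontinuation is described. This stands: what is missing is a label, not the person.

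**Understatement of the proportion is not shown.** A reader might also infer that the non-response percentage is too low. No denominator is stated, the statistical analysis plan is not at hand and may supply one, and step 4 shows either direction is possible. This stands for the proportion, not for the count.

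**Early stopping is narrower than it sounds.** A last injection at about day 122 leads to discontinuation only after day 189 (monthly) or 249 (every other month), past month 6. This stands if the window counts as follow-up.

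**The sentence can be read another way.** Having no VL below 50 during follow-up could be a separate item, which would capture these people. The joint reading is more natural, and if the other was meant the wording needs correcting anyway.

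**An on-treatment response measure is legitimate.** Turning every discontinuation into non-response would create a debatable composite that labels people with no follow-up VL as virologic failures. This stands and shapes the fix. It does not justify leaving observed, never-suppressed early stoppers unlabelled.

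**Conclusion.** The gap is real and follows from the Protocol's own definitions, given the joint reading of the non-response sentence and censoring at discontinuation. A viremic starter who never has a VL below 50 and discontinues before month 6 (or month 12) can be neither a non-responder nor a CVF, so the count of labelled virologic failures in this stratum is short by exactly these people. How many there are cannot be computed from the document. The illustrative 2.2 to 10.0 points rest on assumed counts and on all 229 starters as denominator. The result is descriptive and concerns 229 of 1,843 people (12%) in the two-year data, so this is worth correcting but does not undermine the study.

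**What to change.** Keep the current definition, so that tables already produced stay comparable, and report beside it at months 6 and 12:

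1. **Extended non-response**, which also counts viremic starters with at least one follow-up VL, none below 50, who discontinued before that month.
2. **Discontinued before that month with no follow-up VL**, as a separate category, not merged with non-response.
3. **A stated denominator**: all viremic starters except those administratively censored before that month. It is best to define that exception by index date (too close to study end for the month to be reached), so that late starters are not kept only when they stop. For Year 5, entry runs to 31 December 2025 and observation to 28 February 2026, so such people will exist.

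Also state whether the no-VL-below-50 condition is joint with the month 6 and 12 condition or a separate item, and whether both months are required.

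The cost is wording, slightly more tabulation and a possibly less favourable non-response figure. No new data and no change to treatment or the discontinuation rule are needed. Year 5 preliminary tables are planned for July 2026.

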#### 6.3.2.7 Resistance/Proviral DNA Testing

- Before CVF
  - o N (%) with any genotyping test before CVF
    - N (%) with resistance
      - Types of resistance detected
  - N (%) with proviral DNA test before CVF
    - N (%) with tropism detected
      - Types of tropism detected
- After CVF
  - o N (%) with genotyping test within 4 weeks on/after CVF
    - N (%) with resistance
      - Types of resistance detected
  - N (%) with proviral DNA test within 4 weeks on/after CVF
    - N (%) with tropism detected
      - Types of tropism detected

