#### **Secondary Objectives:**

- 1. Sub-group analyses by viral load (VL <50, ≥50copies/mL) at initiation, BMI (<30 and ≥30 kg/m²) at initiation and age (18-50, 50-64, ≥65 years) at initiation to assess characteristics, adherence, persistence, discontinuation and virologic effectiveness
- 2. To estimate the frequency of documented injection site reactions and hypersensitivity reactions among PWH receiving CAB+RPV LA injections at Year 3, Year 4, and Year 5 of availability
- 3. To compare baseline characteristics and treatment outcomes (persistence/discontinuation, adherence, maintaining virologic suppression, confirmed virologic failure) between oral ART and CAB+RPV LA use in PWH at Year 4 and Year 5 of availability
- 4. To describe baseline characteristics and treatment outcomes (persistence/discontinuation, adherence, virologic effectiveness) among PWH receiving CAB+RPV LA injections at Year 4 and Year 5, in subgroups of interest
  - a. Race/ethnicity (Non-Hispanic Black, Hispanic, Non-Hispanic White)
  - b. Sex/race (Non-Hispanic Black men, Hispanic men, Black women)
- 5. Among individuals with confirmed virologic failure (CVF): to describe HIV resistance and proviral testing at the time of CVF, as well as history of resistance and proviral DNA testing prior to CVF at Year 4 and Year 5 of availability

ViiV Healthcare Protocol Final 216990 – Amendment 2

- 6. Among individuals with confirmed virologic failure (CVF): to describe the ART regimens after CVF in OPERA at Year 4 and Year 5 of availability
  - a. To describe the baseline characteristics (demographic, clinical, treatment patterns) of ART regimen after CVF
  - b. To describe virologic response (suppression, non-response, confirmed virologic failure) to ART regimen after CVF

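### Section 6.3.2.7 splits resistance tests around an undated two-step CVF event, so some tests from the failure episode can be filed as prior history or counted nowhere

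*Protocol*

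**What the plan says.** Secondary objective 5 (Protocol, synopsis and section 5) has two parts: "to describe HIV resistance and proviral testing at the time of CVF, as well as history of resistance and proviral DNA testing prior to CVF".

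Section 6.3.2.7 implements this with two blocks. The before block counts "N (%) with any genotyping test before CVF" and has a matching row for proviral DNA. It has no look-back limit and runs right up to CVF. The after block counts "N (%) with genotyping test within 4 weeks on/after CVF" and "N (%) with proviral DNA test within 4 weeks on/after CVF". No row covers a test later than 4 weeks after CVF.

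Section 6.3.2.6 defines the event. For people suppressed at initiation: "Confirmed virologic failure will be defined as 2 consecutive follow-up VLs ≥200 copies/mL", or alternatively "1 follow-up VL ≥200 copies/mL + discontinuation within 4 months of VL ≥200 copies/mL". For people viremic at initiation, the same two routes apply after a first suppression below 50 copies/mL. There, discontinuation must fall within 4 months for every-other-month dosing "and discontinuation within 2 months for monthly regimen". A second definition for this group repeats the rule at 400 copies/mL.

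Time to failure is to be reported, but the protocol does not say whether the failure date is the first viral load, the second viral load or the discontinuation. It sets no maximum gap between the two viral loads, and does not say whether a resistance test is dated by sample collection or by result.

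**The concern.** Objective 5 depends on separating what was found at failure from what was known before it. The bins in section 6.3.2.7 treat CVF as a single day, while section 6.3.2.6 makes it an episode that can last months. A test ordered because of the failing viral load belongs to that episode whether the sample is the first or the confirmatory one. Under the present bins, its place depends on an unstated date and on the gap between the two steps. At stake are the count of people tested at failure and the content of the history rows, which can absorb tests from the failure itself.

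**Working it through.** The plan gives no figure to reproduce. The check is date arithmetic.

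**Inputs.** At-failure window: day 0 to day 28 after CVF, CVF day included (section 6.3.2.7). History: any day before CVF (same section). Allowance from viral load to discontinuation: 4 months, or 2 months for monthly dosing among those viremic at initiation (section 6.3.2.6). The gap between the two viral loads is not given; 14 to 122 days is assumed.

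**Rule.** Let t = test day − CVF day. If t < 0 the test is before CVF; if 0 ≤ t ≤ 28 it is at failure; if t > 28 it is in neither bin. Put the first qualifying viral load on day 0 and the completing event (second viral load or discontinuation) on day g.

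| CVF dated at | Test on the first failing sample (day 0) | Test at the completing event (day g) |
|---|---|---|
| First viral load, either route | at failure | at failure if g ≤ 28; neither if g > 28 |
| Second viral load | before CVF at every gap | at failure |
| Discontinuation | before CVF whenever g > 0 | at failure |

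**Numbers put in.**
- Two viral loads, g = 61, dated at the second: the first-sample genotype has t = 0 − 61 = −61, so before CVF.
- Same gap, dated at the first: the confirmatory-sample genotype has t = 61 > 28, so neither.
- Discontinuation at the 4-month limit, g ≈ 122, dated at discontinuation: the genotype on the failing sample has t ≈ −122, so before CVF.
- Same case, dated at the viral load: the failing-sample genotype has t = 0 and is counted; a test on the discontinuation day has t ≈ 122, so neither.
- Two viral loads, g = 14, dated at the first: both tests are counted (t = 0 and t = 14).

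**Window against allowance.** One month is 365.25/12 = 30.44 days, so 4 months is 121.75 days and 2 months is 60.9 days. Then 28/121.75 = 23% and 28/60.9 = 46%.

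**Are long gaps plausible on the discontinuation route?** Section 6.3.2.4 defines discontinuation by a lapse of more than 67 days (monthly) or more than 127 days (every other month) since the last injection. Assume it is dated when the lapse is reached, on day 68 or 128, and let d be the days from last injection to the failing viral load. The gap is then 68 − d or 128 − d. Subject to the 2- or 4-month limit, it exceeds 28 days when d < 40 or d < 100 respectively. Such gaps would not be an edge case. The protocol does not confirm this dating.

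**Effect on the counts.** Compare with a window covering the whole episode, with all people with CVF as the denominator. Displacement can only remove people from the tested-at-failure numerator, and only those with no other test in the window. For resistance among those tested, let r of n be resistant. Losing a resistant person gives (r − 1)/(n − 1), which is below r/n when r < n. Losing a non-resistant person gives r/(n − 1), which is above r/n when r > 0. The direction therefore depends on who is displaced.

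**The case against.** The best defence is that the window includes the CVF day itself. If CVF is dated at the first viral load, a genotype on that sample is always counted, on both routes. If it is dated at the second, a genotype on the confirmatory sample is always counted. A person genotyped on both samples is in the tested-at-failure count under either dating. All of this stands. A reader might infer that failing-sample genotypes are generally lost or filed as history; the documents do not support that.

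It can also be said that event dates, and dating by collection or by result, are commonly settled in a statistical analysis plan, which is not shown. That is fair for the date but does not cure the windows. Each row of the table misplaces some failure-episode test, and mixing datings across routes does not help: each route then keeps the fault of the row chosen for it.

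A reader might further infer that treatment-emergent mutations will be reported as pre-existing. The rows are labelled by CVF, not by initiation, and objective 5 asks for neither emergent nor baseline resistance. A test dated before CVF and labelled so is correctly labelled. The lack of a boundary at the first injection makes the history rows less informative but contradicts nothing in the objective.

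**Conclusion.** The point holds in limited form. The two bins do not fit a two-step event, and no single choice of CVF date makes them fit. Some failure-episode tests can land in history, or in neither bin when they fall more than 28 days after the chosen date. The proportion tested at failure can be understated, through people whose only failure-episode test is displaced.

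The number affected cannot be computed: the protocol gives no viral load interval, no genotype timing and no CVF count. A reader might infer that the tables will show too little resistance at failure. That does not follow, because the percentage with resistance among those tested can move either way.

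The conclusion assumes that tests are classed strictly by date, as section 6.3.2.7 reads, and that a test on either qualifying sample or at the discontinuation belongs to the failure. It concerns one secondary, descriptive objective reported at Years 4 and 5. The change should be made because it is cheap and the rows cannot otherwise deliver the split that the objective asks for.

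**What to change.** 1. In section 6.3.2.6, state which event dates CVF on each route and for each definition (200 and 400 copies/mL).
2. In section 6.3.2.7, define at CVF as running from the date of the first viral load that counts toward CVF through 4 weeks after the second viral load or discontinuation that completes it. This interval does not depend on the choice in step 1.
3. End the history rows the day before that first viral load, so that the two categories meet without gap or overlap.
4. State whether tests are dated by sample collection or by result.

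Splitting history at the first CAB+RPV LA injection is a low-cost optional addition. An analysis of newly emergent mutations goes beyond objective 5 and is not required.

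The cost is protocol wording and date logic on data already held; nothing new is collected. The at-failure window will differ in length between people: on the discontinuation route it can reach about 122 + 28 = 150 days, and on the two-viral-load route it has no fixed limit. The tables should say so. The Year 5 preliminary tables are planned for July 2026. If Year 4 tables were produced with the present bins, rerun them or note the change of definition.
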